5.1.3.4 Other imputations

Only PASI and IGA mod 2011 based response variables are imputed with multiple imputation or non-response, other response variables [REDACTED] will be imputed with LOCF.

[REDACTED]

For laboratory test values below Lower Level of Quantification (LLQ) or above Upper Level of Quantification (ULQ) will be imputed as LLQ or ULQ value, respectively. The numerical part of the reported result will be treated as the actual LLQ or ULQ. These laboratory values will be displayed in listings using the standard unit with the reported sign (“<” or “>”).”

5.2 AEs coding/grading

Adverse events will be coded according to MedDRA dictionary. The MedDRA version used for reporting the adverse events will be described in a footnote.

Safety topics of interest, such as risks defined in the Safety Profiling Plan, Risk Management Plan or topics of interest regarding signal detection or routine analysis are defined in the Program Case Retrieval Sheet that is stored in GPS at the path [REDACTED].

5.3 Laboratory parameters derivations

See [Section 2.8.4](#).

5.4 Statistical models

5.4.1 Primary analysis

5.4.1.1 Logistic regression

Binary outcome variables, including PASI [REDACTED] / 90 / [REDACTED] response and IGA mod 2011 0 or 1 response, will be evaluated using a logistic regression model with treatment regimen, body weight stratum and baseline PASI score. Odds ratios will be computed for comparisons between treatment groups utilizing the logistic regression model fitted.

If response rates are 0% or 100% in one of the treatment groups odds ratio estimate and p-values will not be displayed in outputs, but “-” will be shown.

The odds ratio will be calculated such that an odds ratio >1 is favorable for secukinumab. Using PROC GENMOD to calculate the confidence interval for the odds ratios assumes asymptotic normality of the Wald estimate for the regression coefficient. The 95% confidence interval for the regression parameter of the active treatment effect relative to control(s) will be calculated using an exponential transformation to create the confidence interval for the odds ratio.

All p-values reported on linear hypotheses about regression coefficients will be based on the Wald tests from Type III analyses. In the SAS procedure PROC GENMOD, a Type III analysis will be performed by adding the model options: TYPE3, DIST=BIN, and LINK=LOGIT.

Logistic regression will be applied to response variables at each visit.

If logistic regression model does not converge the following steps will be performed:

1. If convergence not reached, remove the covariates from the model one by one until convergence is reached; start with removing baseline body weight, followed by baseline PASI;
2. If convergence not reached, perform Fisher's exact test.

It should be noted that this model might not converge if response rates are too low.

5.4.1.2 Multiple imputations for response variables

Primary and secondary endpoints will be evaluated by Logistic regression and odds ratio estimate as described in the primary analysis method with multiple imputations for missing values. In addition, logistic regression analysis for [REDACTED], PASI 90, [REDACTED] and IGA mod 2011 0 or 1 response by visits will be analyzed using multiple imputation method.

In the multiple imputations analysis the response status will be imputed based on the individual treatment arm information.

Multiple imputation (MI) is a simulation based approach where missing values are replaced by multiple Bayesian draws from the conditional distribution of missing data given the observed data and covariates, creating multiple completed data sets. These completed data sets can then be analyzed using standard methods. [Rubin \(1987\)](#) presented rules how to combine the multiple sets of estimates to produce overall estimates and confidence intervals that adequately incorporate missing data uncertainty.

Missing values for the 'change from baseline PASI score' and 'IGA mod 2011 score' will be imputed simultaneously based on an underlying joint normal distribution and using a Markov Chain Monte Carlo (MCMC) method. The change from baseline in PASI score appears to follow closer to a normal distribution than the actual PASI score. Assuming normality for the 'IGA mod 2011 score' is motivated by [Schaefer \(1997\)](#), where it was shown that the multivariate normal approximation for the imputation of incomplete categorical and binary data is robust.

The imputations will be done separately for each treatment group including baseline weight, failure to at least one previous biologic (yes/no), and number of previous systemic therapies as additional covariates.

Summary statistics for [REDACTED], PASI 90, [REDACTED] and IGA mod 2011 0 or 1 response by visit will be presented in contingency tables with multiple imputations method.

The number of imputations will be set to 100, the seed for the random function will be set to 4572326 for this study. To generate the multiple imputed data sets, the SAS procedure MI can be used as follows:

The input data set <pasi_iga> should have one record per subject with baseline PASI score and IGA mod 2011 score as well as all changes from baseline PASI and post-baseline IGA mod 2011 score.

ODS LISTING CLOSE;

```
ODS OUTPUT MissPattern=msgpat VarianceInfo=varinfo ParameterEstimates=param;
PROC MI DATA=<pasi_iga> OUT=<impdata> SEED=457<studycode> NIMPUTE=100;
VAR <baseline weight> <failure to at least one biologic>
    <number of previous systemic therapies>
    <baseline PASI> <baseline IGA>
    <change from baseline PASI week 1> - <change from baseline PASI week primary endpoint>
    <IGA week1> - <IGA week primary endpoint>;
BY <treatment group>;
RUN;
ODS LISTING;
```

Programming notes:

- The SAS procedure MIANALYZE expects a variable called “_IMPUTATION_” which is generated by the MI procedure. It might be needed to set the SAS option “VALIDVARNAME=UPCASE” temporarily in the program before the MI call, this option should be reset after the MIANALYZE call to VALIDVARNAME=V6.
- In case there are no missings in one treatment group, the MI procedure does not impute any values. In this case the corresponding data need to be imputed manually outside PROC MI and added to the dataset <impdata>.

The imputed data are saved in data set <impdata>. The outcomes of interest, i.e. the PASI /90/ response and IGA mod 2011 0 or 1 response will be calculated, e.g. as follows:

```
DATA <impdata2>;
SET <impdata>;
IF <change from baseline PASI week primary endpoint>/<baseline PASI>=0.90 THEN <PASI 90 response> =1;
ELSE <PASI 90 response>=0;
<...repeat for all PASI response...>

IF <baseline IGA> >=3 THEN DO;
    IF <IGA week primary endpoint> < 1.5 THEN <IGA 0/1 response> =1;
    ELSE IF <IGA week primary endpoint> >=1.5 THEN <IGA 0/1 response> =0;
    ELSE PUT "E" "RROR:" stysid1a=;
END;
ELSE IF <baseline IGA>=2 THEN DO;
    IF <IGA week primary endpoint> < 0.5 THEN <IGA 0/1 response> =1;
    ELSE IF <IGA week primary endpoint> >=0.5 THEN <IGA 0/1 response> =0;
    ELSE PUT "E" "RROR:" stysid1a=;
END;
ELSE <IGA 0/1 response> =0;
RUN;
```

The treatment differences for each imputed data set will then be evaluated by Logistic regression and ODDS ratio as described in [Section 5.4.1.1](#). This analysis will be done by _IMPUTATION_ for the comparison between treatment group. The model should be estimating response probability = 1 by using DESEENDING option. Using the ESTIMATE option in the GENMOD procedure and the ODS OUTPUT data set “Estimates” provides the estimate for the odds ratio and confidence intervals.

```
PROC GENMOD <option>;
CLASS <stratum> <treatment>;
```

```
MODEL <response> = <explanatory variables> / link=logit dist=bin type3;  
BY <by-variables>;  
ESTIMATE "OR. AIN 300 mg q2wVS. 300mg q4w" <treatment> 1 -1/exp;  
ODS OUTPUT Estimates=Estimates;  
RUN;
```

The MIANALYZE procedure expects the parameter estimate in the variables ESTIMATE, and the corresponding standard error in the variable STDERR. Measurements can be obtained from "Estimates" dataset by selecting the row with ODDS ratio estimates.

```
Data <modified dataset>;  
set Estimates;  
if substr(label,1,3)= "Exp";  
ESTIMATE=LBetaEstimate;  
STDERR=StdErr;  
effect= "OR";  
if missing(ESTIMATE) or missing(STDERR) then delete;  
RUN;
```

The estimates and standard errors based on the 100 imputed data are then combined by applying Rubin's rules for multiple imputed data sets, see [Little and Rubin \(2002\)](#).

Programming notes:

- The variables ESTIMATE and STDERR in the input data set for the MIANALYZE procedure may not be missing. Records with missing values need to be deleted and the variable `_IMPUTATION_` needs to be renumbered and regenerated since for each by-group the procedure expects consecutive numbers starting at 1.
- The ESTIMATE and STDERR in terms of odds ratios from logistic regressions will be transformed to follow a normal distribution before MIANALYZE procedure. They will be transformed back to Odds Ratio to get the corrected ESTIMATE and corresponding CIs.

The SAS procedure MIANALYZE will be applied as follows:

Step 1:

```
DATA <modified dataset_t>;  
  SET <modified dataset>;  
  estimate=log(ESTIMATE);  
  stderr=(log(LBETAUPPERCL)-log(LBETALOWERCL))/(2*1.96);  
RUN ;  
  
ODS LISTING CLOSE;  
ODS OUTPUT ParameterEstimates=<results> VarianceInfo=<varinfo> ModelInfo=<modelinfo>;  
PROC MIANALYZE PARMS=<modified dataset>;  
  BY <by-variables>;  
  MODELEFFECTS estimate;  
  Stderr stderr;  
RUN;  
ODS LISTING;  
  
data <results_back>;  
  set <results>;  
  estimate=exp(ESTIMATE);
```

```
LCLMEAN=estimate*exp(-1.96*stderr);
UCLMEAN=estimate*exp(+1.96*stderr);
RUN ;
```

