### **9.4.2 Statistical model, hypothesis, and method of analysis**

The statistical hypothesis for PASI 90 response at Week 16 being tested is that secukinumab 300 mg every 2 weeks is not superior in the proportion of subjects with PASI 90 response at Week 16 versus secukinumab 300 mg every 4 weeks.

The following hypotheses will be tested

$H_1: p_1 - p_0 \leq 0$  versus  $H_{A1}: p_1 - p_0 > 0$ ,

In other words:

H1: secukinumab 300 mg every 2 weeks is not superior to secukinumab 300 mg every 4 weeks with respect to PASI 90 response at Week 16.

The primary analysis method will be the logistic regression model with treatment group and baseline weight, baseline PASI score as explanatory variables. Odds ratio will be computed for the comparison of secukinumab 300 mg every 2 weeks versus secukinumab 300 mg every 4 weeks utilizing the logistical regression model fitted. In case of non-convergence, Fisher's exact test will be applied. Confidence intervals for risk difference will be provided.

The hypotheses H1 will be tested at level 2.5% (one-sided).

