2.5.4 Statistical hypothesis, model, and method of analysis

The statistical hypothesis for PASI 90 response at Week 16 is that AIN457 300mg Q2W is not superior to AIN457 300mg Q4W in the proportion of subjects with PASI 90 response at Week 16.

The following hypotheses will be tested:

$$H_I: p_1 - p_0 \leq 0 \text{ versus } H_{A1}: p_1 - p_0 > 0,$$

In other words:

H_I : AIN457 300mg Q2W is not superior to AIN457 300mg Q4W with respect to PASI 90 response at Week 16

The primary analysis method for PASI 90 at Week 16 will be evaluated using logistic regression model with treatment group, baseline body weight and baseline PASI score as explanatory variables (see [Section 5 Appendix](#)). Odds ratios will be computed for comparisons of AIN457 300mg Q2W versus AIN457 300mg Q4W utilizing the logistic regression model fitted. In case of non-convergence, for analyses with multiple imputation, confidence intervals for risk difference and p-values from the t-test for the risk difference comparing to 0 will be provided; for analyses with non-responder imputation, Fisher's exact test will be performed and confidence intervals for risk difference will be provided.

The hypotheses H_I will be tested at level 2.5% (one-sided).

Details in primary analysis is provided in [Section 5.4.1.1](#) and the sensitivity analysis are provided in [Section 2.5.6](#)

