2.6 Analysis of the key secondary objective

2.6.1 Secondary endpoint

[figure not shown]
The secondary variable in testing strategy is the IGA mod 2011 0 or 1 response at Week 16 (for superiority comparison of AIN457 300 mg Q2W versus AIN457 Q4W). The IGA mod 2011 0 or 1 response at Week 16 will be analyzed analogously to PASI 90 response at Week 16 (i.e., logistic regression analysis).

The analysis of secondary variable will be based on FAS.

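### Three baseline predictors used to impute PASI and IGA scores are left out of the PASI 90 and IGA 0/1 models: a possible, probably small, missed efficiency

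*SAP*

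**What the plan says.** **Imputation model.** SAP 5.4.1.2 imputes change in PASI and IGA score separately by treatment group. Besides baseline weight it takes "failure to at least one previous biologic (yes/no), and number of previous systemic therapies as additional covariates". The PROC MI variable list in the same section also contains "<baseline PASI> <baseline IGA>".

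**Primary model.** SAP 2.5.4 specifies a "logistic regression model with treatment group, baseline body weight and baseline PASI score as explanatory variables". Protocol 9.4.2 has the same three terms: "logistic regression model with treatment group and baseline weight, baseline PASI score as explanatory variables". SAP 5.4.1.1 also lists three terms but describes weight differently: "logistic regression model with treatment regimen, body weight stratum and baseline PASI score".

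**Key secondary model.** Under SAP 2.6.1, IGA 0/1 response at Week 16 "will be analyzed analogously to PASI 90 response at Week 16", so its model has no baseline IGA term. A responder must also improve by at least 2 points from baseline IGA (SAP 2.5.3).

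**Design and data.** Randomization is unstratified (Protocol 5.3, SAP 1.1). Previous psoriasis treatments and reasons for stopping them are recorded at screening, and IGA is recorded at randomization (Protocol 6.2.2 and Table 6-1). SAP 2.3.2 and Table 2-3 already derive previous biologic failure and the number of systemic therapies. The documents give no reason for using these factors in the imputation only.

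**The concern.** The plan regards these variables as useful for predicting PASI and IGA scores, yet neither efficacy model uses them. With no stratification, neither the design nor the analysis deals with chance imbalance in them. If they are prognostic for response, pre-specified adjustment could raise power at no data-collection cost.

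The stake is greatest if the control rate falls below the roughly 70% that Protocol 3.2 cites from the registration studies. The trial's own rationale makes that plausible, since heavier subjects have lower exposure and may have room to improve (Protocol 3.2 and 3.3). IGA 0/1 is tested only if the PASI 90 hypothesis is rejected (SAP 2.6.2), so power for the primary endpoint also governs access to the key secondary test.

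**Working it through.** **1. The planned size.** Inputs from Protocol 9.8 and SAP 3: 165 per arm, a 15-point difference, one-sided 2.5%. Planning power and control rate do not appear in the text. With p̄ the mean of p0 and p1, d = 0.15 and q = 1 − p:

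n per arm = [1.96·√(2p̄q̄) + z_power·√(p0q0 + p1q1)]² / d²

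For 55% vs 70% at 80% power: [1.96 × 0.6847 + 0.8416 × 0.6764]² / 0.0225 = 3.652 / 0.0225 = 162.3, so 163 per arm. The stated 330 also fits 60% vs 75% at 80% power with continuity correction (165 per arm) and 70% vs 85% at 90% (161 per arm). It therefore cannot be tied to one control rate.

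**2. Power with 165 per arm.** Power = Φ{[0.15·√165 − 1.96·√(2p̄q̄)] / √(p0q0 + p1q1)}.

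- 55% vs 70%: (1.927 − 1.342) / 0.676 = 0.865, giving 81%.
- 60% vs 75%: (1.927 − 1.298) / 0.654 = 0.961, giving 83%.
- 70% vs 85%: (1.927 − 1.157) / 0.581 = 1.324, giving 91%.
- Control rates of 40% to 45%: 78%.

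**3. Effect of adding the three covariates.** Each scenario used 2,500 simulated trials of 165 vs 165 with complete data. A logistic model with treatment, weight and PASI was compared with the same model plus biologic failure, number of prior systemics and baseline IGA, using a one-sided Wald test at 2.5%.

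All prognostic inputs are assumptions:
- Odds ratios for biologic failure, per prior systemic, and for IGA 4 vs 3: 1/1/1 (none), 0.7/0.9/0.9 (weak), 0.5/0.8/0.8 (moderate), 0.3/0.65/0.6 (strong).
- Biologic failure in 10% or 30% of subjects; baseline IGA 4 in 40%.
- Weight odds ratio 0.8 per SD and PASI odds ratio 0.9 per SD.

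| Strength | Biologic failure | 55% vs 70%: power | 70% vs 85%: power |
|---|---|---|---|
| None | 10% | 81.0 → 80.4 | 89.9 → 89.9 |
| None | 30% | 80.3 → 80.2 | 91.2 → 91.2 |
| Weak | 10% | 80.4 → 80.9 | 91.0 → 91.2 |
| Weak | 30% | 81.7 → 81.6 | 91.6 → 92.2 |
| Moderate | 10% | 80.8 → 81.8 | 92.0 → 93.1 |
| Moderate | 30% | 81.1 → 83.0 | 91.6 → 92.4 |
| Strong | 10% | 81.8 → 84.7 | 91.5 → 93.7 |
| Strong | 30% | 81.0 → 86.9 | 91.7 → 94.3 |

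The changes are −0.6 to 0 (none), −0.1 to +0.6 (weak), +0.8 to +1.9 (moderate) and +2.2 to +5.9 (strong). Simulation error is about 0.5 to 0.8 points on each power figure; the differences are paired and so more precise.

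**4. Where the gain comes from.** At 55% vs 70% with 30% biologic failure, the standard error of the log odds ratio rises from 0.235 to 0.239 (weak), 0.245 (moderate) and 0.262 (strong). In the strong case the mean estimate moves from 0.665 to 0.801, so the ratio of estimate to standard error goes from 0.665 / 0.2353 = 2.83 to 0.801 / 0.262 = 3.06. Precision does improve on the standardised risk-difference scale when the factors matter: the variance ratio in that case is (0.0484 / 0.0526)² = 0.85. Across scenarios, variance changes by −1% to +1% (weak), −2% to −5% (moderate) and −8% to −15% (strong).

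**5. Cross-checks.** Adding only the two prior-treatment covariates, with 6,000 trials per scenario and other assumed strengths, gave:
- Weak (15% failure, odds ratio 0.5; 0.9 per therapy): +0.3 to +0.4 points.
- Moderate (25%, 0.4; 0.8): 81.2% to 82.9% at 55% vs 70%, and 84.0% to 85.3% at 60% vs 75%.
- Strong (30%, 0.3; 0.75): about +3 points.

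In further simulation, type I error stayed near or below 2.5% with the covariates added, and baseline IGA alone contributed about 1 point at most.

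**The case against.** The strongest reply is that nothing here is wrong. An imputation model richer than the analysis model is accepted practice, and the imputation list shows only that the variables were thought helpful for filling in missing scores. The primary model already contains baseline PASI and body weight, the factor that motivates the trial. Imbalance in the other factors would be visible in the baseline tables. At the only PASI 90 rate the documents cite, about 70%, power is already about 91%. Baseline IGA can only be 3 or 4 in eligible subjects and may overlap with baseline PASI. All of this stands.

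A reader might infer that the plan gives up precision for free. The documents do not support that. The planned effect measure is an odds ratio, and its standard error on the log scale goes up in every scenario when the covariates are added. The estimate also becomes conditional on more factors, and the benefit depends on prognostic strengths that no section gives. Nor is the change costless: the model is fixed in Protocol 9.4.2, SAP 5.4.1.1 applies logistic regression at every visit and warns of non-convergence at low response rates, and its removal order covers only weight and PASI.

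What survives is narrower. The data are already collected, the simulated loss if the factors are not prognostic is at most 0.6 points, and the gain if they are moderate or strong is about 1 to 6 points.

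**Conclusion.** The point holds as an optional improvement of low priority. The three factors are in the imputation model and in neither efficacy model. Adding them would change power by about 0 points if they are weak or not prognostic, 1 to 2 if moderate, and 2 to 6 if strong. The upper end needs both strong effects and a 30% prevalence of biologic failure at a 55% control rate; at 70% the strong case gains only 2.2 to 2.6 points.

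The figures rest on assumed prevalences, odds ratios and control rates, and on complete data. The main simulation includes baseline IGA, which is proposed only for the IGA 0/1 model, so the table may slightly overstate the gain for PASI 90. A reader might also take the difference between the two models as an inconsistency that undermines the primary test. It is not one: no section contradicts another on which of these covariates belong in the analysis, and the present model is valid.

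**What to change.** Before unblinding for the Week 16 analysis:

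- Add prior biologic failure (yes/no) and number of previous systemic therapies to the PASI 90 model in SAP 2.5.4 and 5.4.1.1. State the coding of the count, for example linear or in the groups of SAP Table 2-3 with a zero category.
- Add the same two terms plus baseline IGA (3 vs 4) to the IGA 0/1 model in SAP 2.6.
- Extend the removal order in SAP 5.4.1.1 to cover the new terms. Dropping them first would make the fallback pass through the present model.
- Keep the three-term model as a supportive analysis.
- In the same edit, reconcile the weight stratum of SAP 5.4.1.1, which is not defined, with the baseline body weight of SAP 2.5.4.

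The imputation model needs no change, since it already contains all three variables. If the sponsor prefers the present model, one sentence giving the reason would close the point.

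**Cost:** an amendment to Protocol 9.4.2 with the approvals that Protocol 11.1 requires, two or three extra parameters, an odds ratio conditional on more covariates, and a slightly higher risk of non-convergence, mainly at visits with low response rates. No new data are needed.

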2.5.5 Handling of missing values/censoring/discontinuations

Response variables based on PASI score and IGA mod 2011 categories will be imputed with multiple imputation (MI) as primary imputation method for the missing values (refer to [Section 5.4.1.2](#)).

Multiple imputation (MI) is a simulation based approach where missing values are replaced by multiple Bayesian draws from the conditional distribution of missing data given the observed data and covariates, creating multiple completed data sets. These completed data sets can then be analyzed using standard methods. Within this analysis the PASI score or IGA mod 2011 categories will be imputed and response variables will be derived based on the imputed scores. In the multiple imputation analysis the response status will be imputed based on the individual treatment arm information.

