2.8.4 Laboratory data

The summary of laboratory evaluations will be presented for two groups of laboratory tests (hematology and serum chemistry).

Descriptive summary statistics for the change from baseline to each study visit will be presented by laboratory test and treatment group. Change from baseline will only be summarized for subjects with both baseline and post baseline values and will be calculated as:

$$\text{change from baseline} = \text{post baseline value} - \text{baseline value}$$

Only “on-treatment” laboratory data will be summarized (i.e. assessments within last dose plus 84 days). All laboratory data will be listed with “on-treatment” flag displayed. If two measurements are taken on the same date/time/CRF visit then use the average of two assessments.

For laboratory test values below Lower Level of Quantification (LLQ) or above Upper Level of Quantification (ULQ) will be imputed as LLQ or ULQ value, respectively. The numerical part of the reported result will be treated as the actual LLQ or ULQ. These laboratory values will be displayed in listings using the standard unit with the reported sign (“<” or “>”).

In addition, shift tables will be provided for all parameters to compare a subject’s baseline laboratory evaluation relative to the most extreme laboratory test value within a treatment period. For the shift tables, the normal laboratory ranges will be used to evaluate whether a particular laboratory test value is normal, low, or high (including category “high and low”). These summaries will be presented by laboratory test and treatment group. Subjects with abnormal laboratory values will be listed and values outside the normal ranges will be flagged.

The following laboratory parameters will be analyzed with respect to numerical Common Terminology Criteria for Adverse Events (CTCAE) grades, given in [Table 2-7](#): hemoglobin, platelets, white blood cell count, neutrophils, lymphocytes, creatinine, total bilirubin (TBL),

gamma-glutamyl transferase (GGT), alanine aminotransferase (ALT), aspartate aminotransferase (AST), alkaline phosphatase (ALP).

The number and percentage of subjects with CTCAE grade newly occurring or worsening after baseline will be presented. These summaries will be split into hematology and chemistry.

Table 2-7 CTCAE grades for laboratory parameters to be analyzed

CTCAE v4.0 Term	Grade 1	Grade 2	Grade 3	Grade 4

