2.8.5.3 Vital signs

Analysis in vital sign measurement using descriptive summary statistics for the change from baseline for each post-baseline visit will be performed by vital sign and treatment group. Change from baseline will only be summarized for subjects with both baseline and post-baseline values and will be calculated as:

[figure not shown]
$$\text{change from baseline} = \text{post-baseline value} - \text{baseline value}$$

[figure not shown]
[figure not shown]
[figure not shown]
Only “on-treatment” vital signs will be summarized (i.e. assessments within last dose plus 84 days). All vital signs will be listed with “on-treatment” flag displayed.

[figure not shown]
The number and percentage of subjects with newly occurring notable vital signs will be presented. Criteria for notable vital sign abnormalities are provided in [Table 2-9](#) below. A listing of subjects with newly occurring notably abnormal vital signs will be provided.

Table 2-9 Criteria for notable vital sign abnormalities

Vital sign (unit)	Notable abnormalities
Systolic blood pressure (mmHg)	>= 140 mmHg or < 90 mmHg
Diastolic blood pressure (mmHg)	>=90 mmHg or <60 mmHg
Pulse (bpm)	> 100 bpm or <60 bpm

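### Does the example SAS line in SAP 5.4.1.2 miscode PASI 90 because the sign of PASI change is not stated?

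*SAP*

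**What the plan says.** The endpoint is defined in prose in both documents. SAP 2.5.2 and Protocol 6.4.2 make a PASI 90 responder a subject whose PASI has fallen by at least 90% from baseline.

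Under multiple imputation, SAP 2.5.5 says that "response variables will be derived based on the imputed scores". SAP 5.4.1.2 imputes change from baseline in PASI instead of the score itself, because "The change from baseline in PASI score appears to follow closer to a normal distribution than the actual PASI score". It then shows how response is obtained in the 100 completed data sets. The code is introduced with the words "response and IGA mod 2011 0 or 1 response will be calculated, e.g. as follows", and the key line is "IF <change from baseline PASI week primary endpoint>/<baseline PASI>=0.90 THEN <PASI 90 response> =1", followed by "ELSE <PASI 90 response>=0". The IGA part of the same block contains "ELSE IF <baseline IGA>=2 THEN DO".

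The visible SAP text gives no formula for PASI change. It does give one in two safety sections. SAP 2.8.4 (laboratory data) states "Change from baseline will only be summarized for subjects with both baseline and post baseline values and will be calculated as" the post-baseline value less the baseline value, and SAP 2.8.5.3 (vital signs) states "Change from baseline will only be summarized for subjects with both baseline and post-baseline values and will be calculated as" the same difference.

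**The concern.** Two features of the line catch the eye.

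- **Sign.** The ratio of PASI change to baseline PASI is compared with plus 0.90. With change taken as post-baseline minus baseline, the only direction the visible SAP writes down anywhere, improvement is negative. No true responder could then reach the cut-off, and a patient whose PASI rose by 90% would be coded a responder.
- **Operator.** In "IF <change from baseline PASI week primary endpoint>/<baseline PASI>=0.90 THEN <PASI 90 response> =1" the `>` before the equals sign may close the placeholder or belong to the operator. Spacing does not settle it. "ELSE <PASI 90 response>=0" is an assignment, while "ELSE IF <baseline IGA>=2 THEN DO" is a comparison in the same compressed form.

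This is the only code shown for the primary endpoint, so a literal misreading would affect every PASI 90 result obtained under multiple imputation.

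**Working it through.** **Inputs**

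- PASI 90 definition: reduction of at least 90% (SAP 2.5.2, Protocol 6.4.2).
- Rule in the example code: change / baseline compared with +0.90 (SAP 5.4.1.2).
- Candidate signs: post minus baseline (the form used in SAP 2.8.4 and 2.8.5.3) or baseline minus post.
- Candidate operators: `>=` or `=`.
- Entry minimum PASI 12 (Protocol 4.1) and scale maximum 72 (Protocol 6.4.2).
- PASI 90 around 70% in the registration studies (Protocol 3.2); 165 subjects per arm (Protocol 9.8, SAP 3).

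**Step 1: four readings, baseline PASI 20**

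For example, Week 16 PASI 1 gives (1 - 20)/20 = -0.95 under post minus baseline, and (20 - 1)/20 = +0.95 under baseline minus post.

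| Week 16 PASI | Responder by definition | (post - base)/base | coded by `>=` / `=` | (base - post)/base | coded by `>=` / `=` |
|---|---|---|---|---|---|
| 0 | yes | -1.00 | no / no | +1.00 | yes / no |
| 1 | yes | -0.95 | no / no | +0.95 | yes / no |
| 2 | yes | -0.90 | no / no | +0.90 | yes / yes |
| 3 | no | -0.85 | no / no | +0.85 | no / no |
| 38 | no | +0.90 | yes / yes | -0.90 | no / no |
| 40 | no | +1.00 | yes / no | -1.00 | no / no |

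Only baseline minus post with `>=` matches the definition in all six rows. The other three readings each fail on at least two rows. The definition therefore settles both the sign and the operator.

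**Step 2: the operator**

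The expression follows `IF`, so it is a comparison and not an assignment. An equality test against 0.90 makes no sense for draws from a continuous normal model. In an illustrative simulation with an assumed PASI distribution (true rate about 70%), equality was met by 0.1% of subjects when scores were rounded to 0.1 and by none when they were continuous. A `>` could also have been lost in typing or in reading the PDF.

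**Step 3: would a wrong sign pass unnoticed?**

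Take all pairs on a 0.1 grid with baseline 12.0 to 72.0 and post-baseline value from 0 up to baseline. In tenths there are 601 baselines averaging 420, so there are 601 × (420 + 1) = 253,021 pairs. Of these, 25,573 are reductions of at least 90%. With post minus baseline and `>=`, 0 of the 25,573 are coded responders. That zero is guaranteed, because no ratio is positive when the post-baseline value cannot exceed baseline.

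The count therefore does not measure an effect on the trial, but it shows how crude the failure would be. If the true rate were 70%, about 0.70 × 165 = 115.5 responders per arm would be expected, and the program would return about none. SAP 5.4.1.1 suppresses the odds ratio and p-value when an arm is at 0%. SAP 5.4.1.2 also tabulates imputed PASI 90 rates by visit. The non-responder analysis in SAP 2.5.6, which does not go through the imputed data, would show ordinary rates beside them.

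**Step 4: rounding at exactly 90%**

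The grid has 61 exact 90% reductions (baselines 12.0, 13.0, ..., 72.0). In double precision the unrounded ratio misses 15 of 61 (13.0 to 1.3 gives 0.8999999999999999 in absolute value). Unrounded percent reduction misses 3, and percent reduction rounded to 6 decimals misses none. These are counts of grid points held as decimal fractions in one language. Under SAP 2.5.2 PASI is a weighted sum computed in a separate system whose storage is not described, so the counts do not carry over to patients.

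**The case for a change.** The best argument for acting is that the code step reads the whole imputed data set. The line therefore classifies every subject in all 100 completed data sets, not only those with missing values. It is also to be repeated for the other PASI responses. The block shows signs of reuse from a template: "ELSE IF <baseline IGA>=2 THEN DO" opens a branch for baseline IGA 2, although entry requires 3 or 4, and the seed ends in 2326 while the study is 2324. A plan should not rely on programmers to correct it, one sentence would settle the sign, and an error at the exact 90% boundary would be less visible than a 0% rate.

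Part of this stands. The visible text does not state the sign, a clarifying sentence would do no harm, and rounding before a threshold comparison is sound programming practice. The rest carries less weight. Signs of a template support reading the block as a pattern to adapt, not as a rule that overrides SAP 2.5.2. The failure arises only if a convention from the laboratory and vital-sign summaries is imported into PASI, and nothing in the plan does that. Nor can the sign be called absent from the plan. The public SAP is redacted, its visible sections run from 2.8.5.3 straight to 2.14, and its introduction refers to project standard analysis plans whose details are blacked out.

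**Conclusion.** No change to the plan is needed. The endpoint is stated correctly in both documents, and the example line agrees with it under exactly one of four readings, the one a programmer working from the definition would use. The missing sign is a detail that analysts fill correctly, and the compressed operator is typographic.

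The expected effect on the trial's results is nil: no bias, no change in the endpoint, and no effect on alpha or power. This rests on two assumptions: that programmers treat the prose definition as governing a template introduced as an example, and that PASI 90 rates near zero would be queried in a population where something near 70% is expected.
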